11.0 DETERMINATION OF SAMPLE SIZE

This study will randomize approximately 300 patients to the rapastinel 450 mg and placebo groups in a 1:1 ratio. The sample size is determined based on the primary efficacy endpoint of the change from baseline in the MADRS total score at 1 day after the first dose of treatment. Assuming the SD of the change from baseline in the MADRS total score is 10 points, a sample size of 150 patients per treatment group will provide about 90% power to detect a difference of 3.76 points for a rapastinel dose versus placebo at a 2-sided significance level of 4.9%.

With respect to S-STS total score, 150 patients per arm will provide approximately 88% power for a treatment difference of 4 between rapastinel 450 mg and placebo and estimated standard deviation of 11 based on the blinded analysis in April 2019 at a 2-sided significance level of 4.9%.

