9.7.9 Determination of Sample Size

This study will randomize approximately 300 patients to the rapastinel 450 mg and placebo groups in a 1:1 ratio. The primary efficacy endpoint is the change from baseline in the MADRS total score at 1 day after the first dose of treatment. Assuming the SD is 10 points, a sample size of 150 patients per treatment group will provide 90% power to detect a difference of 3.76 points for a rapastinel dose versus placebo at a 2-sided significance level of 5%.

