Specifically, H1 and H2 will be tested at $\alpha=0.0245$ separately. If H1 is rejected, H3 will then be tested at $\alpha=0.0245$. If H2 is rejected, H4 will then be tested at $\alpha=0.0245$. If H3 is rejected but H2 is not rejected, H2 will be further tested at $\alpha=0.049$. If H2 is rejected at $\alpha=0.049$, H4 will be further tested at $\alpha=0.049$. Similarly, if H4 is rejected but H1 is not rejected, H1 will be further tested at $\alpha=0.049$. If H1 is rejected at $\alpha=0.049$, H3 will be further tested at $\alpha=0.049$.

[REDACTED]

[REDACTED]

[REDACTED]

[figure not shown]
[REDACTED]

[REDACTED]

[REDACTED]

[REDACTED]

[REDACTED]

[REDACTED]

[REDACTED]

[REDACTED]

[REDACTED]

[REDACTED]

[REDACTED]

[REDACTED]

[REDACTED]

[REDACTED]

[REDACTED]

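### SAP power for the two Day-1 primary endpoints is quoted at alpha 0.049, but each is first tested at 0.0245, so 90% and 88% are ceilings under the SAP's own inputs

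*SAP*

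**What the plan says.** SAP Section 9.1 names two primary parameters, both at one day after the first dose: change in MADRS total score and change in S-STS total score. Section 9.2 labels these H1 and H2, labels their Day-28 counterparts H3 (MADRS) and H4 (S-STS), and controls the familywise error over all four at 0.049. That level is what remains of 0.05 after Section 10.6 assigns 0.001 to the interim analysis.

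The 0.049 is then halved: "H1 and H2 will be tested at $\alpha=0.0245$ separately". Rejecting H1 opens H3, and rejecting H2 opens H4, each at 0.0245. A failed H1 is retested at 0.049 only if H4 has been rejected, which requires H2 to have been rejected first. A failed H2 is retested at 0.049 only if H3, and therefore H1, has been rejected.

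Section 11.0 gives power per endpoint. For MADRS (SD 10) it claims "about 90% power to detect a difference of 3.76 points for a rapastinel dose versus placebo at a 2-sided significance level of 4.9" per cent. For S-STS (SD 11, same level) it says "150 patients per arm will provide approximately 88% power for a treatment difference of 4 between rapastinel 450 mg and placebo". It does not mention 0.0245, the retest or any Day-28 assumption.

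**The concern.** The two sections use different levels for the same tests. The power figures belong to a level that neither primary endpoint has at the start and that each can reach only through success elsewhere. Someone planning from Section 11.0 would read 90% and 88% as the chance of success on each primary endpoint. Under the written procedure both chances are lower, by an amount that depends on Day-28 effects and between-endpoint correlations the SAP does not give. At the first step the type II error is about 16% rather than 10% for MADRS and about 19% rather than 12% for S-STS. A non-significant primary result would then be judged against power the design does not guarantee.

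**Working it through.** **Inputs, all from SAP 11.0 and 9.2.** 150 patients per arm, 1:1. MADRS difference 3.76, SD 10. S-STS difference 4, SD 11. Two-sided levels 0.049 (Section 11.0) and 0.0245 (first step, Section 9.2). Like Section 11.0, the check makes no allowance for missing data or covariate adjustment.

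**Noncentrality:** `ncp = difference / (SD × sqrt(2/150))`

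- MADRS: 3.76 / (10 × 0.11547) = 3.256
- S-STS: 4 / (11 × 0.11547) = 3.149

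**Power.** The normal form is `Φ(ncp − z)`, with z = 1.969 at 0.049 and z = 2.249 at 0.0245; the opposite tail is negligible. The t column uses the noncentral t with 298 df.

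| Endpoint | Level | Normal | Noncentral t | SAP 11.0 |
|---|---|---|---|---|
| MADRS | 0.049 | 90.1% | 89.9% | about 90% |
| MADRS | 0.0245 | 84.3% | 84.0% | not given |
| S-STS | 0.049 | 88.1% | 87.9% | about 88% |
| S-STS | 0.0245 | 81.6% | 81.2% | not given |

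The SAP's figures reproduce at 0.049. Moving to the first-step level costs about 6 points for MADRS and 6.5 for S-STS.

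**Detectable difference at 0.0245:** `(2.249 + z_power) × SD × sqrt(2/150)`

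- MADRS, 90% power: (2.249 + 1.282) × 1.1547 = 4.08 points, against 3.76
- S-STS, 88% power: (2.249 + 1.175) × 1.2702 = 4.35 points, against 4

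**Full procedure.** H1 is finally rejected if its p-value is at most 0.0245, or if it is at most 0.049 and both H2 and H4 were rejected at 0.0245. H2 is the mirror image with H1 and H3. The procedure was simulated on z statistics with 1,000,000 draws per scenario. The documents give neither Day-28 effects nor correlations, so these are assumptions. The correlation ρ is 0, 0.3, 0.5 or 0.7 between endpoints at one visit and between visits for one endpoint, and ρ² otherwise. The Day-28 standardised effect is 0, 0.5 or 1 times that of Day 1, or large enough that the Day-28 test always rejects once opened.

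| Day-28 assumption | MADRS Day 1 | S-STS Day 1 |
|---|---|---|
| No effect | 84.3–84.5% | 81.6–81.7% |
| Half the Day-1 effect | 84.7–85.5% | 82.2–83.1% |
| Equal to the Day-1 effect | 86.9–88.2% | 85.2–86.3% |
| Always rejected | 87.6–89.1% | 85.8–87.1% |

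Ranges are over ρ. The comparators by the same normal method are 90.1% and 88.1%, so the shortfall is 90.1 − 89.1 = 1.0 to 90.1 − 84.3 = 5.8 points for MADRS, and 88.1 − 87.1 = 1.0 to 88.1 − 81.6 = 6.5 points for S-STS. None of the 16 scenarios reaches the 0.049 figure. It would be reached only if the other Day-1 and Day-28 tests succeeded in every case where the endpoint's own p-value falls between 0.0245 and 0.049.

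**The case against.** Section 11.0 names its level openly, and both figures are right at that level. 0.049 is the familywise level and one at which Section 9.2 can test H1 and H2, so this could be called an omission rather than a contradiction. That does not help a reader: the figures are offered as the power of the trial, and the conditions for reaching 0.049 are not attached.

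The strongest point is covariate adjustment. The analysis is ANCOVA with baseline, while Section 11.0 uses the SD of raw change. If the baseline–change correlation were about 0.40, the residual SD would fall by about 8% (sqrt(1 − 0.16) = 0.917), and noncentral-t power at 0.0245 would be 90.1% for MADRS and 87.9% for S-STS; at 0.30 it would be 87.5% and 85.0%. This stands as a limit on the claim: the ceilings hold for the unadjusted calculation the SAP presents. But the documents give no such correlation, Section 11.0 does not rely on one, and missing Day-1 data under the observed-case analysis would pull power down.

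The probability of rejecting at least one Day-1 hypothesis is about 91–97% over the assumed correlations. That is reassuring for the trial overall, but Section 11.0 states power endpoint by endpoint.

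Protocol 9.7.9 also gives 90% for 3.76 points, at 5%, with MADRS Day 1 as the sole primary endpoint. It is not a clean single-test benchmark, because Protocol 9.7.5.2 applies Hochberg across the primary and key secondary endpoints. The finding rests on the SAP alone.

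**Conclusion.** The concern holds. Under the SAP's own differences, SDs and sample size, the written procedure does not deliver the power stated in Section 11.0. The 90% and 88% are upper bounds, and the first-step figures of about 84% and 81% are lower bounds. Where the true values fall between them depends on Day-28 effects and correlations the SAP leaves unstated; over the range assumed here the shortfall is about 1 to 6 points per endpoint. This assumes 150 evaluable patients per arm and no gain from ANCOVA. Familywise error control, the order of testing and the treatment estimates are not affected. It should be corrected, but it is a fault in the power statement and not in the testing procedure.

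**What to change.** Replace the two power statements in SAP 11.0 with text along these lines:

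> At the initial two-sided level of 0.0245, 150 evaluable patients per arm give about 84% power for 3.76 points on MADRS (SD 10) and about 81% for 4 points on S-STS (SD 11), without covariate adjustment. At 0.049, which applies only once the other Day-1 endpoint and its Day-28 endpoint have both been rejected, the figures are about 90% and 88%. On the same unadjusted basis, marginal power under the full graphical procedure lies between these values and depends on the Day-28 effects and the correlations.

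Then state the Day-28 effects and correlations the sponsor assumes and the simulated power they imply. If gain from baseline adjustment is to be counted, state the assumed baseline–change correlation too.

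The cost is one paragraph and a short simulation, and the stated power becomes less favourable. Enrolment and the testing rules stay as they are.

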12.0 STATISTICAL SOFTWARE

Statistical analyses will be performed using [REDACTED].

13.0 STATISTICAL AND DATA HANDLING CONVENTIONS

13.1 Summary Statistics

The following statistical summaries will be presented for each type of data. Further details are specified in the tables, figures, and listings shells.

- Continuous variables will be summarized by descriptive statistics (number of patients, mean, standard deviation (SD), median, minimum, and maximum values).
- Categorical variables will be summarized by frequency distributions (counts and percentages).
- Time-to-event data will be summarized by showing the number of patients, number of patients experiencing the event of interest, estimates of the median, 1st quartile and 3rd quartile using the Kaplan Meier estimate as well as a 95% CI for the median.

13.2 Visit Windows

Table 13.2–1 presents the visits assigned for efficacy and safety analyses and the corresponding range of treatment days (window) during which an actual visit may occur.

Table 13.2–1. Visit Windows

Analysis Visit	Target Date	Analysis Window (Based on Date)
Day 0 (Baseline)	IndexA ^a	Last record on or before IndexA ^a
Hour 4	IndexA ^a	(IndexA ^a , 6 hours after IndexA ^a]
Day 1	IndexA ^a +1	(6 hours after IndexA ^a , IndexA ^a +1]
Day 4	IndexA ^a +4	[IndexA ^a +2, IndexB ^b -1]
Day 7	IndexB ^b	IndexB ^b
Day 8	IndexB ^b +1	[IndexB ^b +1, IndexC ^c -1]
Day 14	IndexC ^c	[IndexC ^c , IndexD ^d -1]
Day 21	IndexD ^d	[IndexD ^d , IndexD ^d +3]
Day 28	IndexD ^d +7	[IndexD ^d +4, day of final double-blind visit or early-termination visit occurring after IndexD ^d +3]
Day 35	IndexD ^d +14	Within the safety follow-up phase

a IndexA: Date of the first dose

b IndexB: Date of the second dose or IndexA+7 if the second dose was not administered

- c IndexC: Date of the third dose or IndexB+7 if the third dose was not administered or IndexA+14 if both the second and the third dose were not administered
- d IndexD: Date of the fourth dose or IndexC+7 if the fourth dose was not administered or IndexB+14 if both the third and the fourth dose were not administered or IndexA+21 if the second, third and fourth dose were not administered
- e [REDACTED], the visit windows for Days 0 and 7 will be extended to cover the next dosing day (IndexB and IndexC, respectively); the visit window for Day 21 will be IndexD to the last double-blind visit, inclusively.

If a patient has 2 or more non-missing assessments within the same window, the assessment closest to the target day will be used for analysis; if there are 2 closest assessments with the same number of days from the scheduled day, the later one will be used for analysis.

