9.0 EFFICACY ANALYSES

All efficacy analyses will be based on the mITT Population, unless stated otherwise. The baseline for each specific efficacy endpoint is defined as the last non-missing measurement prior to the first dose of randomized treatment during DBTP.

For efficacy analyses in which study center is a factor, a small center will be defined as a center with < 2 patients in ≥ 1 treatment group in the mITT Population. Small centers will be pooled to form pseudo-centers so that each treatment group includes ≥ 2 mITT patients within the center. Pooling will be done using the following algorithm:

Based on the number of mITT patients, small centers will be ordered from the largest to the smallest, and centers of the same size will be ordered from the largest center code to the smallest center code. The pooling process starts with the largest small center from the top, which will be pooled with the smallest from the bottom until a non-small center is formed. The process will be repeated using the small centers left out after the first pass. If any centers are left out at the end of the process, they will be pooled with the smallest pseudo-center. If there is > 1 smallest pseudo-center, the pseudo-center with the smallest center code will be selected. In case the pseudo-center formed by pooling all small centers is still a small center, it will be pooled with the smallest non-small center. If there is > 1 smallest non-small center, the one with the smallest center code will be selected. These pseudo-centers will be used for all efficacy analyses when the model is adjusted for study center. The efficacy analyses using the mITT Population will be performed based on the treatment to which the patient is randomized regardless of the actual treatment received.

The efficacy analyses of MADRS assessments will be based on the rater-administered MADRS. The MADRS total score is the sum of the 10 individual items. If more than 2 items are missing, then the total score will be set to missing. If there are multiple assessments of MADRS total score for the same nominal visit of a participant, only the last assessment will be used in the analysis.

The efficacy analyses using the mITT population will be performed based on the treatment to which the patient is randomized regardless of the actual treatment received.

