13.4 Repeated or Unscheduled Assessments of Safety Parameters

If a patient has repeated assessments before the start of the first treatment, the results from the last non-missing assessment made prior to the start of the IP will be used as baseline. If end-of-study assessments are repeated or if unscheduled visits occur, the last non-missing postbaseline assessment will be used as the end-of-study assessment for generating summary statistics. However, all postbaseline assessments will be used for PCS value determinations, and all assessments will be presented in the data listings.

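### Does the SAP's visit-window table let a post-dose rating serve as the baseline?

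*SAP*

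**What the plan says.** Table 13.2-1 in SAP 13.2 assigns records to analysis visits.

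- The window column is headed "Analysis Window (Based on Date", and footnote a reads "IndexA: Date of the first dose".
- The Day 0 (Baseline) row is "Last record on or before IndexA".
- The Hour 4 window opens just after IndexA and closes "6 hours after IndexA". The Day 1 window opens there and runs to IndexA+1. The Day 4 window starts at IndexA+2.
- If a window holds several records, the one closest to the target day is used. If two are equally close, "the later one will be used for analysis".
- Footnote e makes an exception for a measure whose name is redacted: "the visit windows for Days 0 and 7 will be extended to cover the next dosing day".

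The baseline is also defined outside the table. SAP 9.0 gives it, for each efficacy endpoint, as the "last non-missing measurement prior to the first dose of randomized treatment during DBTP". SAP 13.4 says of safety parameters that the "last non-missing assessment made prior to the start of the IP will be used as baseline". The protocol synopsis and protocol 9.7.5 also place the baseline before the first dose.

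**The concern.** A window that includes the dosing date includes all of it, before and after the injection. Protocol 9.1.2 puts Visit 3 at 4 hours after the first dose, and protocol 9.2 plans efficacy assessments at every visit. A post-dose MADRS and S-STS rating on the dosing date is therefore to be expected. The Day 0 row takes the last qualifying record, which would be that one, and the tie rule also leans towards the later record. SAP 13.2 does not say that Section 9.0 takes precedence.

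The stakes would be real if the row were applied that way. Day 0 supplies the baseline for both primary change scores and the covariate in both ANCOVAs (SAP 9.1). A 4-hour score in that role would remove from the comparison any treatment effect already present at 4 hours. It would also have a different look-back: protocol 9.5.1.2 uses 1 week at Screening and Baseline, and the time since the last evaluation at all later ratings.

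The second worry is the hour limits. A date has no clock time from which to count 6 hours, so the boundary between Hour 4 and Day 1 looks undefined.

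**Working it through.** The plan states no figure to reproduce. The check applies each possible meaning of IndexA to the same records and sees which one the table can bear.

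**Inputs.** The windows and tie rule come from SAP 13.2. Visit 3 is at 4 hours and Visit 4 at 1 day (protocol 9.1.2). A first dose at 09:00 is assumed for illustration, with ratings at 08:00 (1 h before), 13:00 (4 h after), and 08:00 or 10:00 the next day (23 h or 25 h after).

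**Readings.**

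- A: IndexA is the whole calendar day, so hours count from its end.
- B: IndexA is midnight at the start of that day.
- C: IndexA is the dose date and time in every row, so IndexA+1 means 24 h later.
- D: IndexA is the dose time for Day 0 and the 6-hour limits, and the +n limits are calendar days.

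| Rating | A | B | C | D |
|---|---|---|---|---|
| 08:00, pre-dose | Day 0 | Day 1 | Day 0 | Day 0 |
| 13:00, 4 h | Day 0 | Day 1 | Hour 4 | Hour 4 |
| Next day 08:00, 23 h | Day 1 | Day 1 | Day 1 | Day 1 |
| Next day 10:00, 25 h | Day 1 | Day 1 | none | Day 1 |

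**Which readings can be meant.**

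- A puts the Hour 4 window at 00:00 to 06:00 on the day after dosing (00:00 + 6 h), where it cannot catch a 4-hour rating after a morning dose. That row would be pointless.
- B leaves Day 0 and Hour 4 without any of the example ratings and puts a pre-dose rating in Day 1.
- C leaves a hole from 24 h to 48 h, because Day 1 ends at IndexA+1 and Day 4 starts at IndexA+2. It also ignores the column heading and the tie rule, both of which work in days.
- D places every example rating once, in the window its visit implies.

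**Overlap of Day 0 and Hour 4.** Day 0 closes at IndexA and Hour 4 opens just after it. If IndexA has one meaning in both rows, no record can meet both. An overlap appears only if IndexA is a whole day in the first row and a clock time in the second. Its length is then the time from dose to midnight: 24 − 8 = 16 h for an 08:00 dose, 24 − 18 = 6 h for an 18:00 dose. Those hours reflect the assumed dose time and measure no effect on the analysis.

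**Baseline.** SAP 9.0 names the baseline for the efficacy endpoints directly, so the ANCOVA covariate does not need the Day 0 row. The word *on* in that row has an ordinary purpose. Protocol 9.4.1 has the product given after all assessments except the specified post-dose ones, so the usual baseline rating falls on the dosing date. *Before* covers the case in protocol 9.1.2 where a Screening rating no more than 1 day old stands in for Baseline.

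**Day 1 outcome.** The target is IndexA+1. Counted in days, a Visit 4 rating on that date is 0 days away and any dosing-day rating is 1 day away. The closest-record rule therefore takes Visit 4 under A, B and D, provided a Visit 4 rating exists.

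**Data.** Protocol 9.4.11 captures the date and time of each injection. Visits 2 and 3 are separate visits in protocol 9.1.2, so a Visit 3 rating can be recognised as post-dose from its visit label.

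**The case for a change.** The strongest case for changing the table is that the SAP says it serves both efficacy and safety analyses, never ranks it below Section 9.0, and leaves the workable reading unstated. Reading D mixes clock time and calendar days, so a programmer has to infer it. The obvious repair, making IndexA a date and time throughout, is reading C, and it would leave a Visit 4 rating at 25 h in no window. The primary analysis uses observed cases without imputation, so that patient would drop out of it. Two programmers starting from different sections could build different datasets, and the correction costs only a few words.

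What stands is that footnote a is imprecise and the Day 0 row is looser than the definition in Section 9.0. The step to a wrong dataset does not stand. To get a post-dose baseline, an analyst would have to set aside the explicit definition in SAP 9.0, which protocol 9.7.5 and the synopsis support, in favour of a general windowing row read in a way that empties the next row. To lose a 25 h rating, the analyst would have to read limits set in days as limits in hours. Nor is it true that the 6-hour limits cannot be computed: they follow from the injection time that the protocol collects. The visible text does not show whether a clock time is recorded for every rating scale, but the visit label separates Visit 2 from Visit 3 without one.

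**Conclusion.** No change to the plan is needed. This is a slip in a table footnote that analysts will settle from the rest of the plan: baseline is pre-dose, the 6-hour limits run from the injection, and the day limits are calendar days. Read that way, the covariate and outcome of both primary ANCOVAs are the pre-dose rating and the Visit 4 rating, as intended, with no loss of records and no bias.

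The loose wording touches 3 of the table's 10 rows (Day 0, Hour 4 and Day 1). No change in power, type I error or the estimated difference has been shown, and the documents do not hold the inputs to calculate one.

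The conclusion rests on two assumptions. First, the specific definition in SAP 9.0 governs over the general table; the SAP does not say so, but the protocol agrees with it. Second, MADRS and S-STS are rated at Visit 3. That is inferred from protocol 9.2 and the existence of an Hour 4 row, because the Schedule of Evaluations is not visible. If they are not rated then, the main source of a post-dose baseline disappears.

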Consent and screening procedures are to be conducted in an inpatient setting for suicidality (see Inclusion Criterion #3). After providing written consent, patients will enter a screening period of no more than 5 days. Every effort should be made to conduct all procedures as early as possible in the Screening. Patients will not receive any investigational product (IP) during the screening period. Treatment for suicidality should proceed per local SOC with limited restrictions ([Section 9.4.9.1](#)).

Efforts should be made to minimize the length of the Screening Period and proceed to randomization or screen failure as rapidly as clinically reasonable. Patients meeting the eligibility criteria at Assessment/Visit 2 (Baseline) will be assigned a treatment by the interactive web response system (IWRS) and enter the DBTP.

9.1.2 **Double-blind Treatment Period**

Patients will be randomized in a ratio of 1:1 to 1 of 2 treatment groups: rapastinel 450 mg IV weekly injection or placebo IV weekly injection. During participation in the study, patients may be treated per local SOC with limited restrictions (see [Section 9.4.9.1](#)) and IP will be administered in addition to SOC treatments.

Naurex

There will be 4 study visits during the first week of the DBTP:

- Visit 2: Baseline IP dosing

Note: If Baseline is ≤ 1 day since Screening assessments were conducted, specified Baseline assessments do not need to be repeated and Screening assessments will count as Baseline (see Section 9.5.5.2 for details).

- Visit 3: 4 hours following the baseline IP dosing
- Visit 4: 1 day following the baseline IP dosing
- Visit 5: 4 days following the baseline IP dosing

There will be 2 study visits during the second week of the DBTP:

- Visit 6: 7 days following Visit 2
- Visit 7: 1 day following Visit 6

There will be 3 weekly study visits during the remainder of the DBTP:

- Visit 8: 14 days following Visit 2
- Visit 9: 21 days following Visit 2
- Visit 10: 28 days following Visit 2

If necessary, study visits may be conducted up to 2 days before or after the scheduled visits except for Assessment/Visit 3 (which must be conducted approximately 4 hours after Visit 2), Visit 4 (which must be conducted 1 day after Visit 2), and Visit 7 (which must be conducted 1 day after Visit 6). All patients who receive IP must complete Visit 10 or Early Termination (ET) Visit.

[figure not shown]

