9.4.6 Selection and Timing of Dose for Each Patient

The IP will be administered IV using the assigned single-use prefilled syringes at Visits 2, 6, 8, and 9.

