9.2 Secondary Efficacy Analysis

The two key secondary efficacy parameters are:

[figure not shown]
- Change from baseline in MADRS total score at 28 days after first dose of treatment
- Change from baseline in S-STS total score at 28 days after first dose of treatment

Analysis of change from baseline in MADRS total scores and change from baseline in S-STS total score will be performed using mixed-effects model for repeated measures (MMRM) with terms for treatment, study center, visit, baseline, and treatment-by-visit and baseline-by-visit interactions. An unstructured covariance matrix will be used to model the covariance of within-patient scores. The Kenward-Roger approximation will be used to estimate denominator degrees of freedom (Kenward et al, 1997). The treatment difference for rapastinel versus placebo at selected timepoints will be estimated and reported along with the corresponding 95% CI and the p-value for superiority testing.

In the case that the MMRM with unstructured covariance fails to converge with the default algorithm, then the Fisher scoring algorithm will be used to provide better initial values of the covariance parameters; if the model still does not converge, a simplified model without term for study center will be used to find the initial values of the covariance parameters. In the rare event that model still does not converge after using those initial values, simplified covariance structures will be used to fit the model in the following order: (1) ante-dependence, (2) heterogeneous autoregressive, (3) Toeplitz, and (4) compound symmetry. If MMRM still fails to converge, by visit ANCOVA model similar to the primary efficacy analysis will be used for the analysis.

Let H1 and H2 represent the treatment effect comparisons of rapastinel with placebo in regards to the primary efficacy parameters of change from baseline in MADRS total score and change from baseline in S-STS total score at 1 day after first dose of treatment, respectively; and let H3 and H4 represent the treatment effect comparisons of rapastinel with placebo in regards to the secondary efficacy parameters of change from baseline in MADRS total score and change from baseline in S-STS total score at 28 days after first dose of treatment. The graphical procedure displayed in [Figure 9.2-1](#) will be employed to control the overall familywise error rate at $\alpha=0.049$.

Figure 9.2-1. Graphical Testing Procedure

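### SAP Table 13.2–1 times the Day 28 window from the fourth dose, not the first, so a few permitted visit timings mislabel a completer's Visit 10 rating

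*SAP*

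**What the plan says.** SAP 9.2 names two key secondary parameters: "Change from baseline in MADRS total score at 28 days after first dose of treatment" and "Change from baseline in S-STS total score at 28 days after first dose of treatment". They are H3 and H4 in the graphical testing procedure.

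Protocol 9.1.2 counts the late visits from the first dosing visit: "Visit 9: 21 days following Visit 2" and "Visit 10: 28 days following Visit 2". It also allows some movement: "If necessary, study visits may be conducted up to 2 days before or after the scheduled visits". The exceptions are Visits 3, 4 and 7, so Visits 6, 8, 9 and 10 may move. Protocol 9.4.6 fixes the dosing visits: "The IP will be administered IV using the assigned single-use prefilled syringes at Visits 2, 6, 8, and 9".

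SAP Table 13.2–1 uses dose dates as anchors. IndexA is the first-dose date. IndexB and IndexC come from the second and third doses, with fallbacks in 7-day steps when a dose is not given. For the last anchor, footnote d begins: "IndexD: Date of the fourth dose or IndexC+7 if the fourth dose was not administered". The Day 21 window is IndexD to IndexD+3. The Day 28 window opens at IndexD+4, has its target at IndexD+7 and has no fixed last day. When a window holds several ratings, the one nearest the target is used, and a tie goes to the later one.

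**The concern.** The endpoint is defined by time since the first dose, but the label that decides which rating supplies it depends on when, or whether, the fourth dose was given. A patient can attend Visit 10 inside the protocol tolerance and still have no Day 28 value, or have a Visit 9 rating analysed as Day 28.

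This affects endpoints under error control. In SAP 9.2, rejecting H3 allows an unrejected H2 to be retested at 0.049, and rejecting H4 does the same for H1. The Day 28 data can therefore also bear on the two Day 1 primary hypotheses.

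A second question is what *second*, *third* and *fourth dose* mean in footnotes b to d. They could be the doses scheduled at Visits 6, 8 and 9, or the nth dose the patient received. Protocol 9.4.11 provides for injections that do not take place, so the case can arise, and two programmers could build different Day 28 datasets from the same text.

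**Working it through.** **Inputs.** Days are counted from the first dose (IndexA = Day 0). With ±2 days, Visit 6 is on Days 5–9, Visit 8 on Days 12–16, Visit 9 on Days 19–23 and Visit 10 on Days 26–30 (Protocol 9.1.2). Windows and fallbacks are from SAP 13.2. The Schedule of Evaluations is not visible in the text, so I assume both scales are rated at Visits 8, 9 and 10.

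**The table on schedule.** With doses on Days 0, 7, 14 and 21, IndexD = 21. The Day 28 target is 21+7 = 28 and the window opens at 21+4 = 25. Every permitted Visit 10 (Days 26–30) is labelled Day 28, so the table works as intended here.

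**When Visit 10 leaves the window.** There is no fixed last day, so only the lower edge can exclude it. Visit 10 is excluded if its day ≤ IndexD+3.
- Visit 10 on Day 28: excluded if IndexD ≥ 25, a fourth dose at least 4 days late and outside tolerance. With all doses inside ±2 days this happens in 0 of 125 timings.
- Visit 10 on Day 26: excluded if IndexD ≥ 23, which is within tolerance.

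**Case (i), IndexD = 23 and Visit 10 on Day 26.** The rating is at IndexD+3, the last day of the Day 21 window, so Day 28 is empty. IndexD = 23 arises in two ways:
- The fourth dose is given on Day 23. The Day 21 target is then Day 23. Visit 9 is at distance 0 and Visit 10 at distance 3, so the Visit 10 rating is discarded. Of the 5 × 5 = 25 Visit 9/Visit 10 day pairs, only (23, 26) has a gap of 3 days or less: 1 of 25. Over all 5 × 5 × 5 × 5 = 625 timings of Visits 6, 8, 9 and 10 this is 25.
- The fourth dose is missed after a Visit 8 dose on Day 16: IndexC = 16, IndexD = 16+7 = 23. A Day 26 Visit 10 again misses Day 28. It loses to a Visit 9 rating made on Day 23. If Visit 9 was earlier, the Visit 10 rating is used as the Day 21 value.

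**Case (ii), fourth dose missed and IndexD = 19.** A Visit 8 dose on Day 12 gives IndexD = 12+7 = 19. The Day 28 target becomes 19+7 = 26 and the window opens at 19+4 = 23. A Visit 9 rating on Day 23 is at distance 3 and a Visit 10 rating on Day 30 at distance 4, so Visit 9 supplies the Day 28 value. This occurs in 5 of 625 timings.

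**Missed doses under the two readings, with all other doses and visits on their nominal days.**

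| Doses given (days) | IndexD, scheduled-dose reading | IndexD, nth dose received | Label of a Day 28 Visit 10 (scheduled / received) |
|---|---|---|---|
| 0, 7, 14 | 21 | 21 | Day 28 / Day 28 |
| 0, 7, 21 | 21 | 28 | Day 28 / Day 21 |
| 0, 14, 21 | 21 | 28 | Day 28 / Day 21 |
| 0, 14 | 21 | 28 | Day 28 / Day 21 |
| 0, 21 | 21 | 35 | Day 28 / Day 14 |

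On the scheduled-dose reading, a missed dose by itself moves nothing. On the received-dose reading, missing only dose 2 or only dose 3 takes Visit 10 out of Day 28 in 600 of 625 permitted timings.

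**Check of the remedy.** Take the target as IndexA+28 and, for illustration, the nominal lower bound IndexA+25. Visit 10 (Days 26–30) is then inside Day 28 in 625 of 625 timings, for every missed-dose pattern and both readings. Visit 9 (at latest Day 23) is outside. The present table with all doses given achieves 600 of 625.

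**The case against.** Dose-based windows may be deliberate. Protocol 9.4.1 has product given after the assessments, so windows starting on a dosing day keep the Day 7, 14 and 21 ratings pre-dose, and Day 28 then sits about a week after the last dose. That is a sound reason for Days 7 to 21. It does not carry over to Day 28, where no dose is given and SAP 9.2 counts from the first dose.

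Case (i) with all doses given needs Visit 9 on its latest permitted day and Visit 10 on its earliest, and the protocol allows shifts only when necessary. The other cases also need a missed fourth dose. This stands and limits the size. So does the point that a moving target rarely matters, because Visit 10 is usually the only rating in the Day 28 window. The rule is the same in both blinded arms, nothing here shows bias in a particular direction, and a patient without a Day 28 value still contributes other visits to the MMRM.

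On the dose terms, the scheduled-dose reading has good support. Protocol 9.4.6 ties doses to visits, each index is attached to a scheduled day, and footnote c's mention of both the second and third doses being missed would be redundant if doses were counted as received. On the other side, the multi-dose fallbacks list only runs of final doses, the only patterns possible when counting received doses, and SAP 8.1 summarises patients by number of doses received. The SAP neither states nor excludes either reading.

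**Conclusion.** The mismatch of anchors is on the face of the documents, and in a few permitted timings it discards or replaces a completer's valid Visit 10 rating for H3 and H4. The point is worth correcting, but it is limited.

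A reader might infer that late or missed doses generally push an on-time Visit 10 out of Day 28. The documents do not support that. With doses inside ±2 days, a Visit 10 held on Day 28 is never lost, and on the scheduled-dose reading a missed dose alone changes nothing. The large missed-dose effect depends entirely on the received-dose reading and should be treated as an ambiguity to close, not as what the SAP prescribes.

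A reader might also turn 1 of 25 into 4% of patients, or 0.04 × 150 = 6 per arm. That would require visit days to be uniform and independent, and all 150 to reach Visit 10. The fractions count calendar timings, not patients. The documents give no frequency of late visits, missed doses or dropout, so the number affected cannot be stated. It is probably small. The working assumes both scales are rated at Visits 8, 9 and 10.

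**What to change.** Before unblinding, amend SAP 13.2 as follows:
- Set the Day 28 target to IndexA+28.
- Always assign the Visit 10 rating of a patient who completes the double-blind period to Day 28.
- End the Day 21 window before that visit and keep Visit 9 ratings out of the Day 28 window. For example, Day 28 could open at IndexA+25 and Day 21 run up to the day before, so that a Day 23 Visit 9 is not left unassigned.
- Restate the early-termination entry against the new lower bound.
- State in footnotes b to d that the second, third and fourth doses are those scheduled at Visits 6, 8 and 9.

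The dose-indexed windows for Days 7 to 21 can otherwise stay. The cost is SAP wording and window programming; no new data are needed.
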